This study is a prospective observational study. Three drops of heel peripheral blood samples were collected from 2000 newborns, and 24 genes of 29 NHB-related genetic diseases were analyzed. All dry blood spot samples that met the inclusion criteria could be included in the genetic analysis. At the same time, the clinical data of these 2000 newborns were collected, and the daily jaundice monitoring at home was performed using the percutaneous jaundice meter (YSJ-20). The data were synchronized to the mobile phone jaundice follow-up doctor assistant small program for storage statistics. The family members can view the jaundice risk level and obtain free doctor consultation in the small program.

The purpose of this study is to study the carrying rate of pathogenic genes of common hereditary jaundice diseases in newborns, to understand whether there is a difference in the carrying rate of pathogenic genes in different degrees of jaundice, to explore whether there is a difference in the degree of jaundice carrying multiple and single jaundice pathogenic genes, and to analyze the correlation between gene polymorphism and clinical manifestations (phenotypic polymorphism) of neonatal hyperbilirubinemia, so as to evaluate the feasibility of jaundice gene screening program in the detection of jaundice-related genetic metabolic diseases.

Based on the 'Classification Criteria and Guidelines for Genetic Variation (2017)', the variation pathogenicity of genetic testing is divided into five categories : known pathogenic, possible pathogenic, unclear significance, possible benign and benign. In this study, known pathogenic and possible pathogenic are classified as positive results. The pathogenicity of the mutation site is mainly based on the pathogenic mutation database and the latest literature reports.

The classification criteria of jaundice were based on the American Academy of Pediatrics (AAP) 2022 edition of neonatal hyperbilirubinemia management guidelines for gestational age ≥ 35 weeks and the latest version of 2023 guidelines to interpret the management of neonatal hyperbilirubinemia-the diagnosis and intervention criteria of neonatal hyperbilirubinemia in the American Academy of Pediatrics and multi-national clinical management guidelines. The 2000 neonates were divided into 500 cases of non-

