significant hyperbilirubinemia ($TSB / TCB < 205\text{umol} / \text{L}$), 500 cases of significant hyperbilirubinemia ($205\text{umol} / \text{L} \leq TSB / TCB < 342\text{umol/L}$), 500 cases of severe hyperbilirubinemia ($TSB/TCB \geq 342\text{umol/L}$) and 500 cases of extremely severe hyperbilirubinemia ($TSB/TCB \geq 428\text{umol} / \text{L}$).

4. Inclusion criteria

- (1) Informed consent of parents or guardians ;
- (2) Age : 1-28 days, gestational age ≥ 35 weeks ;
- (3) Birth weight ≥ 2.5 kg and < 4 kg.

5. Excluded criteria

- (1) Neonatal data with unclear clinical basic information ;
- (2) Lack of traceability core information data ;
- (3) data that the test results cannot be analyzed and interpreted ;
- (4) Sample collection is not qualified and unwilling to cooperate with re-sampling.
- (5) Newborns with severe deformity and severe lethal inherited metabolic diseases

6. termination criteria

- (1) The family members of the newborn included in the study requested termination at any time ;
- (2) The relevant management departments require termination.

7. outcome index

Through the comprehensive analysis of genetic variation information and jaundice clinical data, the carrying rate of pathogenic genes of common hereditary jaundice diseases in newborns was counted, and the difference of carrying rate of pathogenic genes in different degrees of jaundice was understood. To explore whether there is a difference in the degree of jaundice carrying multiple and single jaundice pathogenic genes, and to analyze the correlation between gene polymorphism and clinical manifestations (phenotypic polymorphism) of neonatal hyperbilirubinemia.

8. Grouping and sample size

This study is a prospective observational study. According to the positive mutation rate of NHB-related genes in neonatal hyperbilirubinemia, P is about 30 %, the test level α

= 0.05 and the allowable error $\delta = 2 \%$, n (sample size) = ($U\alpha / \delta$) $2 * p * (1 - P) \approx$ 2000 cases. A total of 2000 neonates were included, including 500 cases of non-significant hyperbilirubinemia ($TSB / TCB < 205\text{umol} / L$) ; (2) 500 cases of significant hyperbilirubinemia ($205\text{umol} / L \leq TSB / TCB < 342\text{umol} / L$) ; (3) 500 cases of severe hyperbilirubinemia ($TSB / TCB \geq 342\text{umol} / L$) ; (4) Extremely severe hyperbilirubinemia 500 cases ($TSB / TCB \geq 428\text{umol} / L$) .

9. Recruiting

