This study will recruit subjects in the outpatient and inpatient departments of pediatrics, neonatology, and obstetrics in the South China Neonatal Genetic Screening Alliance (including cooperation units of 49 hospitals).

10. Clinical evaluation index

- (1) The carrying rate, positive rate, negative rate and high-frequency mutation sites of common NHB-related gene mutation sites in neonates ;
- (2) The difference in the carrying rate of NHB-related pathogenic genes in neonates with different degrees of jaundice ;
- (3) The difference of jaundice degree between carrying multiple and single jaundice pathogenic genes ;
- (4) Gene-gene interaction and genotype-phenotype correlation.

11. Methods

11.1 gene sequencing

A total of 24 genes were included in 29 NHB-related genetic diseases, including bilirubin metabolic disorders, congenital bile acid synthesis or transport disorders, red blood cell metabolic defects, lipid metabolic abnormalities, and metal metabolic abnormalities. The detected genes included ABCB11, ABCB4, ABCC2, ABCD3, ACOX2, AKR1D1, AMACR, ATP7B, ATP8B1, CYP7B1, G6PD, GBA, HBB, HSD3B7, JAG1, NOTCH2, NPC1, NPC2, NR1H4, SLC10A1, SLC25A13, SMPD1, TJP2 and UGT1A1. Gene and genetic disease related information refer to OMIM and Orphanet database.

Target gene sequence capture and library construction. Three drops of heel peripheral

blood were collected by filter paper, and genomic DNA was extracted by magnetic bead method. The target gene sequence was captured by multiplex PCR amplification method, covering all exon regions and adjacent intron regions ($\pm 50\text{bp}$) of the target gene. A total of 900 amplicons were designed for 24 genes and completed in two amplification systems. The target sequence library was obtained after amplification-purification-re-amplification-re-purification. The library was quantified using a Qubit[®] 3.0 fluorescence quantitative instrument (Thermo Fisher Scientific), and the library length was determined using an Aglient 2100 biological analyzer (Agilent) (228-378 bp).

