11.2 Information and data collection

Researchers should truthfully fill in the test results of the subjects and other relevant information, and ensure that the information is true and reliable. The specific

information and data to be collected are as follows :

(1) Sign informed consent ;

(2) Jaundice gene detection : Take out the special filter paper blood collection card, disinfect with alcohol and dry the heel blood collection site, collect heel peripheral blood, drop three drops on the filter paper.

(3) Detection of jaundice value by percutaneous jaundice meter : The family members of the subjects rented the percutaneous jaundice meter for free under the guidance of the doctor, and used the ' single measurement mode ' to measure the forehead, chest and inner thigh of the subjects every day for a total of 2 weeks.

(4) Collect demographic characteristics : screening number, name, gender, gestational age, date of birth, birth weight, body length, head circumference, mode of conception, Apgar score and parental information ;

(5) Perinatal information : parity, parity, mode of delivery, fetal membranes, amniotic fluid, placenta, umbilical cord, intrauterine distress, group B streptococcal infection, pregnancy complications such as gestational hypertension, diabetes, etc.

(6) Jaundice information : parents and newborns blood type, hemolysis three tests, feeding methods, percutaneous jaundice value, jaundice treatment and related test results ;

(7) Gene detection results : Collect gene analysis results, notes, etc.

12. Statistical processing

IBM-SPSS 26.0 statistical software and R language (Version 4.1.0) were used for statistical analysis of the test results. The carrying rate of common NHB-related gene mutation sites in neonates was counted, and the differences in the carrying rate of NHB-related pathogenic genes in neonates with different degrees of jaundice were compared. To explore the difference in the degree of jaundice carrying multiple and single jaundice-related genes. The measurement data were expressed as mean \pm standard deviation ($x \pm s$), and the t test was used for comparison between groups. The count data were expressed as values or rates (%), and the chi-square test was used for comparison between groups. Unconditional logistic multivariate regression analysis

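### Genotype is read only from heel blood, and the plan neither times the sample relative to transfusion nor flags post-transfusion spots, so some genotypes could be donor or mixed, with bias in either direction.

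*Combined protocol and SAP*

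**What the plan says.** **DNA source.** Section 11.1 describes one source, heel blood on filter paper: "blood were collected by filter paper, and genomic DNA was extracted by magnetic bead method". Section 11.2(2) gives the sampling steps ("disinfect with alcohol and dry the heel blood collection site, collect heel peripheral blood, drop three drops on the filter paper") without placing them before or after any treatment. No buccal or other non-blood sample is planned.

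**Which spots are used.** Section 3: "All dry blood spot samples that met the inclusion criteria could be included in the genetic analysis". The inclusion criteria (section 4) are consent, age, gestational age and birth weight. The age criterion opens "Age : 1-28 days, gestational age", so entry is possible on any day of the first four weeks.

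**Who is recruited.** Section 9 names the "outpatient and inpatient departments of pediatrics, neonatology, and obstetrics" of an alliance of 49 hospitals. Section 8 sets a quota of 500 infants at or above 428 umol/L.

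**Safeguards.** Section 5 excludes (3) "data that the test results cannot be analyzed and interpreted" and (4) "Sample collection is not qualified and unwilling to cooperate with re-sampling". Section 11.1 adds Sanger sequencing of the parents' loci for two kinds of result: autosomal recessive double heterozygotes and autosomal dominant single heterozygotes.

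**Treatment data.** Section 11.2(6) collects "percutaneous jaundice value, jaundice treatment and related test results". Section 12 does not use treatment to flag, exclude or re-examine a genotype. Transfusion is not mentioned in the protocol.

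**The concern.** A spot taken after an exchange or red-cell transfusion may contain donor DNA, depending on how the blood product was prepared. The genotype could then be the donor's, or a mixture that reads as an extra heterozygous variant. Consent comes before sampling (section 16) and inpatients are eligible, so an infant may already have been treated when the spot is taken.

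If such infants are more common in the top severity group, the genotyping error is related to the grouping variable. Two of the four evaluation indices in section 10 depend on that relation: index 2 compares carriage across grades, and index 3 compares jaundice between carriers of several genes and carriers of one. A mixed sample can also turn a single-gene carrier into an apparent multiple-gene carrier. Section 14 foresees families learning positive results and receiving genetic counselling, so a donor-derived call could reach a family.

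**Working it through.** **1. The plan's own figure.** Section 8 uses n = (U/δ)² × P × (1 − P) with P = 0.30, α = 0.05 and δ = 0.02. With two-sided U = 1.96 this gives about 2017, so the stated figure of about 2000 reproduces. The 95% half-width at P = 0.30 is 2.0 points for n = 2000 and 4.0 points for one group of 500. This calculation neither depends on the present point nor is changed by it.

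**2. Do the safeguards catch a post-transfusion spot?**
- Exclusion (4) concerns how the sample was collected. A post-transfusion spot can be collected properly.
- Exclusion (3) concerns results that cannot be read. A visibly mixed result might be removed here, but no criterion for mixed DNA is given, and a donor genotype can be perfectly readable.
- The parental Sanger check could expose a donor variant that neither parent carries. It does not extend to single heterozygotes for recessive variants, who count towards carriage, and it cannot show an infant variant masked by donor DNA.

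**3. Possible size.** Nothing in the documents gives the inputs, so these are assumptions:
- true carriage 45% in the extremely severe group and 30% in a comparison group;
- donor carriage 30% (the plan's 30% is a positive rate in neonatal hyperbilirubinemia, borrowed here for illustration);
- a share f of the 500 top-group infants affected, and none in the comparison group.

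Replacement (donor genotype only): observed rate = 0.45(1 − f) + 0.30f.

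Mixing (donor and infant variants both called): an affected infant tests positive with probability 1 − 0.55 × 0.70 = 0.615, so observed rate = 0.45(1 − f) + 0.615f.

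The odds ratio is taken against 0.30/0.70. With no infant affected it is (0.45/0.55)/(0.30/0.70) = 1.91, and the difference is 15 points.

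| f (infants) | Replacement: rate | Difference (points) | OR | Mixing: rate | Difference (points) | OR |
|---|---|---|---|---|---|---|
| 5% (25) | 44.25% | 14.3 | 1.85 | 45.8% | 15.8 | 1.97 |
| 10% (50) | 43.5% | 13.5 | 1.80 | 46.7% | 16.7 | 2.04 |
| 20% (100) | 42.0% | 12.0 | 1.69 | 48.3% | 18.3 | 2.18 |
| 30% (150) | 40.5% | 10.5 | 1.59 | 50.0% | 20.0 | 2.33 |

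**4. What this does to a test of 500 against 500** (two-sided 0.05, normal approximation).
- Replacement: power for 45% against 30% is about 99.9%. It is about 99% at f = 10% and about 94% at f = 30%. With a smaller true difference, 40% against 30%, it falls from 91% to 88%, 85% and 76% at f = 5%, 10% and 20%.
- Mixing with no true difference (30% in both groups): an affected infant tests positive with probability 1 − 0.70 × 0.70 = 0.51. The top-group rate becomes 31.1%, 32.1% and 34.2% at f = 5%, 10% and 20%, and the false-positive rate 6.5%, 11.1% and 29.6% instead of 5%.

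**5. Overall carriage rate.** With four groups of 500, a shift confined to one group moves the overall rate by a quarter as much. The 4.2-point shift in step 4 (34.2% − 30%) becomes about 1.05 points. The comparison between grades is more exposed than the overall rate.

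**The case against.** The strongest reply is that the premise is outside the documents. Transfusion is never mentioned, and the share transfused, the timing of sampling and the donor DNA content are all unknown. Leucocyte-depleted blood would lessen the effect. The study is prospective with two weeks of daily monitoring, so some infants may be sampled before their peak or before treatment. All of this stands, and it is why no estimate of the actual bias is possible.

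A reader might infer four stronger things that the documents do not support:
- *That every spot is accepted after any treatment.* Section 3 says spots could be included, exclusions (3) and (4) still apply, and the rest is inferred from silence.
- *That transfused infants are known to cluster in the top group.* This is a reasonable clinical inference without a documented rate.
- *That the bias is towards no difference.* This holds only for replacement. Mixing raises apparent carriage.
- *That sample and transfusion times will not be captured.* Section 11.2 lists categories of data, and the case report form is not in the documents.

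It is also fair to say that, with a true difference as large as 45% against 30%, replacement barely threatens detection. The odds ratio would still be misstated, and that comfort does not extend to smaller differences or to mixing. None of these replies supplies a rule that identifies an affected genotype.

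**Conclusion.** The point holds as a gap in specimen handling whose effect is uncertain in size and direction. Followed as written, the plan could analyse donor or mixed genotypes as the infant's own, and its safeguards would catch only some of them.

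Under the stated assumptions (45% against 30% true carriage, 30% donor carriage, 5 to 30% of the top group affected, none in the comparison group), an odds ratio of 1.91 could be observed anywhere from 1.59 to 2.33. At 5% affected the range is 1.85 to 1.97, which is minor. If few infants are transfused before sampling, or the blood carries little donor DNA, the effect is negligible. The plan as written does not commit to collecting what would show which case applies. Indices 2 and 3 are exposed, the overall carriage rate much less so, and the sample size calculation is unaffected.

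**What to change.** In section 11.2(2):
- record the date and time of the heel sample and of any blood-product transfusion;
- genotype from a spot taken before transfusion where one exists and consent covers its use;
- flag any genotype obtained from a post-transfusion spot.

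In section 12, prespecify a sensitivity analysis of indices 2 and 3 without the flagged infants, and report their number by severity group.

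The flagged infants should not simply be dropped from the main analysis. On the range above that could remove 25 to 150 of the 500 in the top group, possibly the most severely affected, and so introduce a selection bias of its own. A sensitivity analysis shows whether the conclusion depends on them.

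The cost is a little more data entry (none if the case report form already holds these times), a few sentences in the protocol and one extra analysis. The times should be captured prospectively, because they may be hard to recover across 49 hospitals. The change concerns the research specimen and its analysis only, not care.

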individual differences in age of onset and clinical manifestations. Even if the same pathogenic gene mutation is carried out, the clinical phenotype can be different. Therefore, the application of genetic testing in this type of disease can improve the early diagnosis of the disease. Genetic testing of children without jaundice or hospitalized jaundice can obtain the proportion of genetic factors and their genotypes in children with jaundice, so as to continuously improve the efficiency of disease diagnosis.

However, previous studies have focused on the role of one or two specific genes in patients with hyperbilirubinemia. For example, a number of studies have shown that the UGT1A1 gene hotspot c.211G > A polymorphism is a risk factor for NHB, and is closely related to the severity of jaundice, and can aggravate the symptoms of breast milk jaundice, glucose-6-phosphate dehydrogenase deficiency, hereditary spherocytosis, and hemolytic jaundice caused by congenital erythropoietic anemia. Yang et al. showed that the c.211G > A locus was a risk factor for severe hyperbilirubinemia in patients with glucose-6-phosphate dehydrogenase deficiency. Watchko et al. showed that a single G6PD gene mutation or UGT1A1 gene mutation only caused mild jaundice, but the coexistence of the two mutations may cause severe NHB or even nuclear jaundice. Up to now, there is no literature report on the study of gene polymorphism and clinical manifestation polymorphism of jaundice in large data population.

The transcutaneous jaundice instrument (YSJ-20) has obtained the ' People 's Republic of China Class II Medical Device Registration Certificate '. It can accurately, quickly, safely and non-invasively detect the current bilirubin level of the newborn through the skin appearance. It is portable, easy to operate, and has a low threshold for use. It is very suitable for family members to monitor the level of neonatal jaundice at home.

In summary, this study intends to collect heel peripheral blood samples from 2000 newborns [including 500 non-significant hyperbilirubinemia newborns, 500 significant hyperbilirubinemia newborns, 500 severe hyperbilirubinemia newborns and 500 extremely severe hyperbilirubinemia newborns]. The gene capture sequencing

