technology containing 24 genes of neonatal common hereditary jaundice genes was used to detect and collect the clinical data of these 2000 newborns. At the same time, the percutaneous jaundice meter (YSJ-20) was used to monitor the daily jaundice at home. According to the analysis results of gene detection and clinical data of jaundice in 2000 children, the carrying rate of pathogenic genes of common hereditary jaundice in neonates was studied, and the carrying rate of pathogenic genes in different degrees of jaundice was understood. Whether there is a difference in the degree of jaundice with multiple and single jaundice pathogenic genes, and the correlation between gene polymorphism and clinical manifestations (phenotypic polymorphism) of neonatal hyperbilirubinemia were analyzed.

2. Research objective

(1) To analyze the carrying and pathogenicity of neonatal jaundice-related genes, and to collect the sequencing data of jaundice-related genes (24 genes of 29 NHB-related genetic diseases) of 2000 newborns in the cooperative hospital, and to complete the construction of the gene database.

(2) To analyze the incidence of NHB-related genes, pathogenic mutations, suspected pathogenic mutations, and the carrying rate of unknown mutations in 2000 cases, and to count the distribution of high-frequency variation sites in the population, so as to provide a scientific basis for the selection of mutation sites for large-scale neonatal hyperbilirubinemia gene screening.

(3) The influence of jaundice-related genes on neonatal jaundice was analyzed. The clinical data of newborns and the daily percutaneous bilirubin level were collected through the hospital hospitalization system and the " percutaneous jaundice instrument home monitoring + software doctor-patient interconnection " method, and the construction of intelligent neonatal jaundice clinical database was completed.

(4) Analyze the integrated monitoring data, statistically analyze the gene and jaundice data of 2000 newborns, understand whether there is a difference in the carrying rate of related pathogenic genes in different degrees of jaundice, and explore whether there is a difference in the degree of jaundice carrying multiple and single jaundice pathogenic genes. To understand the correlation between gene polymorphism and clinical manifestations (phenotypic polymorphism) of neonatal hyperbilirubinemia, thereby increasing the accuracy of genetic diagnosis.

3. Research Design

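### The overall carrying rate and site frequencies describe an equal four-group bilirubin mix, not newborns or infants with hyperbilirubinemia, and the ±2 points in section 8 is not tied to any of these.

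*Combined protocol and SAP*

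**What the plan says.** Section 8 (Grouping and sample size) bases the sample size on one proportion: "According to the positive mutation rate of NHB-related genes in neonatal hyperbilirubinemia, P is about 30 %, the test level α" = 0.05, with an allowable error of 2 points, giving about 2000. The same section then sets the allocation: "A total of 2000 neonates were included, including 500 cases of non-significant hyperbilirubinemia", with 500 more in each of the significant, severe and extremely severe groups.

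The overall rate is planned separately from the group rates:

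- Section 7 (outcome index): "the carrying rate of pathogenic genes of common hereditary jaundice diseases in newborns was counted".
- Section 10, index (1), and section 12 also refer to neonates without limiting the rate to the study sample. Section 12 only counts the rate.
- Section 2, objective (2), is mixed. One clause is tied to the sample ("the carrying rate of unknown mutations in 2000 cases"). The next counts "the distribution of high-frequency variation sites in the population, so as to provide a scientific basis for the selection of mutation sites" for large-scale screening.
- Section 2, objective (4), and section 10, index (2), ask "whether there is a difference in the carrying rate of related pathogenic genes in different degrees of jaundice".

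Neither the protocol nor its statistical section gives sampling fractions, shares of the four groups among births, weights or standardisation. Nothing limits the overall rate to the study mix.

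**The concern.** Sampling by bilirubin level is a sound way to compare severity groups. It also means that the make-up of the sample is set by the design and not by how often each severity occurs. A pooled count then gives the extremely severe infants a quarter of the weight, whatever their share among births.

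The pooled rate is therefore not a newborn rate. It is not clearly the rate behind the 30% either, because that figure is for neonatal hyperbilirubinemia and a quarter of the sample is the group below 205 µmol/L. Once the groups are fixed, section 8 does not say which rate the ±2 points describes.

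The pooled figure equals a newborn figure only if carriage is the same in all groups, or by coincidence. The plan gives reason not to assume equality. Section 1 states that the "UGT1A1 gene hotspot c.211G > A polymorphism is a risk factor for NHB, and is closely related to the severity of jaundice", and objective (4) sets out to test for differences.

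At stake is the use of index (1) and objective (2). A reader could take the quota-mix rate or site ranking as a population figure and choose screening sites from it.

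**Working it through.** **Inputs from section 8:** P = 0.30, α = 0.05 (taken as two-sided, z = 1.96), δ = 0.02, four groups of 500.

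**1. The plan's own figure.** n = (z/δ)² × P(1−P) = (1.96/0.02)² × 0.21 = 2016.8, rounded up to 2017. The stated figure of about 2000 reproduces. A one-sided z gives 1421 and does not.

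**2. What each set of infants delivers at P = 30%.** Half-width = 1.96 × √(0.21/n):

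| Set | n | Half-width (points) |
|---|---|---|
| Equal four-group mix | 2000 | ±2.01 |
| Three groups at or above 205 µmol/L | 1500 | ±2.32 |
| One bilirubin group | 500 | ±4.02 |

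**3. Pooled rate against a hyperbilirubinemia rate.** Let p₁ be the rate in the lowest group and m the mean rate of the other three. The four-group rate is (p₁ + 3m)/4, so it differs from m by (p₁ − m)/4. A gap of 8 points shifts it by 2 points.

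**4. Pooled rate against a newborn rate, for any newborn mix.** With disjoint groups and representative recruitment within each, the pooled rate is the plain mean of the four group rates. A newborn rate lies somewhere between the lowest and highest of them. The error is therefore at most 0.75 × (highest − lowest). To guarantee 2 points, the spread must not exceed 2/0.75 = 2.67 points. The difference between two groups of 500 has a half-width of 1.96 × √(2 × 0.21/500) = 5.68 points, so a non-significant comparison would not establish so small a spread.

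**5. Illustration with assumed figures.** The documents give no carrying rates by group. Their only newborn severity figure is 60% to 80% with some jaundice (section 1). The newborn mixes assumed here, lowest to highest group, are A 50/45/4.5/0.5%, B 70/28/1.8/0.2% and C 40/50/8/2%. All rate patterns pool to 30%. Bias = 30 − Σ(share × rate), in points:

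| Assumed group rates (%) | A | B | C |
|---|---|---|---|
| 30/30/30/30 | 0 | 0 | 0 |
| 28/30/31/31 | 0.95 | 1.38 | 0.70 |
| 31/31/30/28 | −0.94 | −0.98 | −0.86 |
| 20/28/34/38 | 5.68 | 7.47 | 4.52 |

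Example, last row, mix A: 0.50×20 + 0.45×28 + 0.045×34 + 0.005×38 = 24.32, and 30 − 24.32 = 5.68.

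An intermediate pattern of 25/28/32/35% under mix A gives 12.5 + 12.6 + 1.44 + 0.175 = 26.72, a bias of 3.3 points. The 2-point error is thus exceeded under the two steeper assumed gradients and not under the shallow ones.

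**6. Precision of a reweighted rate.** With all rates at 30%, the half-width is 1.96 × √(Σ share² × 0.21/500): A ±2.71, B ±3.03, C ±2.59 points.

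**The case against.** The strongest reply has five parts.

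- **The sample may be all that is meant.** Objective (2) ties a rate to the 2000 cases, and the protocol also calls its participants newborns and neonates. Its use of population could mean the study population. This ambiguity is real. It does not remove the purpose clause, since choosing sites for large-scale screening reaches beyond the sample on either reading.
- **All four groups carry the name hyperbilirubinemia**, the lowest being labelled non-significant, so 30% may be meant for all 2000. The 1500-infant reading is then only one possibility. The background phrase "Genetic testing of children without jaundice or hospitalized jaundice" is weak evidence for the other side, since it is a general remark and not an eligibility rule. Even so, an equal four-group mix is not shown to match the natural severity mix of hyperbilirubinemia.
- **The evidence for a gradient is limited.** The UGT1A1 statement concerns one locus in a 24-gene panel. Section 1 also reports that a single G6PD or UGT1A1 mutation caused only mild jaundice, with severe disease linked to the two together. This stands, and it is why no direction of bias is claimed.
- **Group rates are already planned, and section 11.1 annotates variants with external population frequencies.** Both are true. The annotation does not weight the study counts, and index (1) and objective (2) still rest on pooled figures.
- **A figure of ±4.0 per group assumes 30% in every group.** Correct: 1.96 × √(p(1−p)/500) gives ±3.5 at 20% and ±4.3 at 38%. The figure should be quoted with its assumption.

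**Conclusion.** The concern holds and should be fixed. The arithmetic of section 8 is right. What is wrong is that the sized quantity, the sampled mix and the rate to be reported are three different things, and the plan does not say so.

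What follows from the documents' figures is ±2.01 points for the equal mix and ±4.02 points per group at 30%. The limit of 0.75 × the spread in group rates needs no assumed newborn mix, but it does require disjoint groups and representative recruitment within each.

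The actual bias is unknown in size and direction and could be zero; the figures in points rest on assumed rates and mixes. The between-group comparisons in index (2) are not affected. The feasibility evaluation in sections 3 and 18 draws on several aims and on correlation analysis, so it is touched only where it uses the overall rate or the site ranking.

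**What to change.** 1. In section 8, state a precision of about ±4.0 points per bilirubin group of 500 at P = 30%, and say that ±2 points applies only to the equal four-group study mix.
2. For index (1) and objective (2), report carrying rates and site frequencies by bilirubin group as the result. Label any pooled rate or site ranking as describing the study mix only.
3. Make a population or screening-site statement only from an estimate weighted by an external severity distribution of births, with stratified variance. Without such weights, make no such statement.

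Step 3 has two limits. Weights need disjoint strata, so the severe (≥342) and extremely severe (≥428) definitions, which overlap as written, must be reconciled first; that is a separate defect. Weighting also does not correct for non-random recruitment within groups from outpatient and inpatient departments (section 9).

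Steps 1 and 2 cost wording and tables only: no extra infants, tests or between-group analyses. Step 3 needs severity counts that the documents do not show to exist, and only if a population statement is wanted. The price is a less favourable stated precision: about ±4.0 points per group, or roughly ±2.6 to ±3.0 points for a reweighted rate under the assumed mixes.
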